## 3.1.2 Experience with Ad35-GRIN

Ad35-GRIN is a replication-incompetent recombinant Adenovirus serotype 35 expressing HIV-1 Clade A genes (*gag, reverse transcriptase, integrase* and *nef* (GRIN). The GRIN genes were identified within the HIV-1 sequence, designed as a fusion product, and codon-optimized for human cell expression and translation. GRIN was selected based on the evidence that in a worldwide study assessing HIV-1-infected humans, the highest levels of T-cell responses (75-100%) were observed against gag, pol, and nef, regardless of either the donor's origin or the subtype of the infecting virus . Where appropriate, mutations have been introduced to abrogate the normal functions of the HIV proteins.

The recombinant adenovirus (rAd) vaccine design is based on the concept of immunisation by gene transfer. Following entry into target cells, it is expected that the HIV-1 gene products will be expressed without the production of infectious adenovirus particles or integration into the host genome and stimulate predominantly CD8+ cytotoxic T cells to the HIV-1 proteins. Preclinical studies and clinical studies   show that immune responses against HIV can be elicited by direct gene transfer of immunogen-expressing HIV genes via recombinant

#### CONFIDENTIAL

adenovirus vectors. The major advantage of rAd immunization appears to be its efficacy in transducing host cells and priming the induction of CD8+ cytotoxic T lymphocytes (CTL) responses, which are considered important in limiting viral replication. There is an additional safety feature in that following entry into the target cells, the HIV-1 gene products will be expressed without the production of infectious adenovirus (Ad) or integration into the host genome. These gene products can be produced in cells that are not actively dividing.

A second vector has been produced which contains the HIV-1 subtype A gp140 gene (Ad35-ENV), although it will not be used in this trial. Non-human primate immunogenicity data suggest that stronger HIV-specific CD8+ T cell responses are generated by Ad35-GRIN/ENV at a dosage of  $2 \times 10^{10}$  vp and  $2 \times 10^{11}$  than at lower dosage levels.

A Phase I placebo-controlled, double-blinded (in terms of vaccine or placebo), randomized dose-escalation trial to evaluate the safety and immunogenicity of Ad35-GRIN/ENV HIV Vaccine in 42 healthy adult volunteers is ongoing in the US (IAVI B001 - BB-IND# 13876). Three vaccine dosages are tested:  $2 \times 10^9$ ,  $2 \times 10^{10}$ , and  $2 \times 10^{11}$  viral particles (vp). The vaccine is administered by intramuscular route at months 0 and 6. As of 17 December 2009, safety data is available for the first 42 injections of vaccine or placebo in all dose groups, with 13 and 8 receiving the 6-month booster dose in the  $2 \times 10^9$  and  $2 \times 10^{10}$  groups respectively. Overall, the Ad35-GRIN/ENV vaccine was generally safe and well tolerated. The high dose of Ad35-GRIN/ENV at 2x10^11 vp appeared more reactogenic both systemically and locally compared to the low  $(2x10^9 \text{ vp})$  and mid  $(2x10^{10} \text{ vp})$  dose groups, with 5/14 volunteers in the high dose group reporting severe, but transient, systemic reactions after the first vaccination. No serious adverse event has been reported in either group. No Ad35 shedding was reported in the few samples tested to date. These preliminary data suggest that the  $2x10^{11}$  vp dose may be likely to cause transient but moderate-severe systemic reactions. Therefore the 2x10^10 vp dose was selected for this study.

See Ad35-GRIN/ENV Investigator Brochure for full description of the preclinical and clinical safety profile of this candidate vaccine.

#### 4.0

## STUDY OBJECTIVES

#### 4.1 **Primary Objectives**

#### Safety

- To evaluate the safety and tolerability of F4co formulated in AS01B or AS01E and Ad35-GRIN in the following regimen:
  - $\circ~$  F4co formulated in AS01\_B or AS01\_E followed by Ad35-GRIN
  - Ad35-GRIN followed by F4co formulated in AS01B

 F4co formulated in AS01B co-administered (simultaneous administration with separate injections) with Ad35-GRIN

## Immunogenicity

- To evaluate the immunogenicity of F4co formulated in AS01B or AS01E
  - $\circ~$  To demonstrate the non-inferiority of the immune response (in terms of the magnitude of the CD4+ CD40L+ T cells expressing at least IL-2) to F4co formulated in AS01E compared to F4co formulated in AS01B at 2 weeks post second dose (Groups A and B)

## 4.2 Secondary Objectives

## Immunogenicity

- To evaluate the immunogenicity of F4co formulated in AS01B or AS01E and Ad35-GRIN
  - To evaluate the immunogenicity of two doses of F4co formulated in  $AS01_B$  and  $AS01_E$  followed by a single Ad35-GRIN boost (Groups A and B) at 4 weeks and one year post-boost.
  - $\circ$  To evaluate the immunogenicity of a single Ad35-GRIN prime followed by two doses of F4co formulated in AS01B (Group C) at 4 weeks and one year post-second F4co.
  - $_{\odot}$  To evaluate the immunogenicity of 3 doses of co-administered F4co formulated in AS01\_B and Ad-35 GRIN (Group D) at 4 weeks and one year post-third dose.
  - To evaluate the immunogenicity of two doses of F4co formulated in  $AS01_B$  (Group B) or in  $AS01_E$  (Group A) at 4 and 12 weeks post-second F4co, a single dose of Ad35-GRIN (Group C) at 4 and 12 weeks post-Ad35-GRIN, and two doses of co-administered F4co formulated in  $AS01_B$  and Ad-35 GRIN (Group D) at 4 weeks post-first co-administration, 4 and 12 weeks post-second co-administration.

## 5.0

## STUDY ENDPOINTS AND STUDY DESIGN

## 5.1 Study Endpoints

## 5.1.1 Primary Endpoints

Safety and tolerability:

- Proportion of volunteers with solicited adverse events (any OR any grade 3 or above) during a 14 day (Day 0 to Day 14) follow-up period after each vaccination
- Proportion of volunteers with unsolicited adverse events (any OR any grade 3 or above OR any related event OR any grade 3 or above and related) during a 4 week (Day 0 to Day 28) follow-up period after each vaccination and over the whole vaccination period

- Proportion of volunteers with abnormal biochemical and haematological values (any grade 3 or above) after each vaccination and throughout the study period
- Proportion of volunteers with serious adverse events (any event OR any related event) throughout the study period

#### Immunogenicity:

 To assess non-inferiority: magnitude of the CD4+ CD40L+ T cells expressing at least IL-2 to F4co formulated in AS01E, and F4co formulated in AS01B

## 5.1.2 Secondary Endpoints

Immunogenicity:

- Proportion of volunteers with HIV-1 specific T-cell responses measured by IFN- γ and IL-2 ELISPOT assay at indicated time points after stimulation with HIV-1 Clade A and B peptide pools matched to the vaccines
- Magnitude of HIV-1 specific T-cell responses measured by IFN- γ and IL-2 ELISPOT assay at indicated time points after stimulation with HIV-1 Clade A and B peptide pools matched to the vaccines
- Proportion of volunteers with HIV-1 specific CD4+ or CD8+ T-cell responses assessed by Intracellular Cytokine Staining measuring IL-2 and / or IFN- γ and/or TNF-α at indicated time points after stimulation with HIV-1 Clade A and B peptide pools matched to the vaccines
- Magnitude of HIV-1 specific CD4+ or CD8+ T-cell responses assessed by Intracellular Cytokine Staining measuring IL-2 and / or IFN- $\gamma$  and/or TNF- $\alpha$  at indicated time points after stimulation with HIV-1 Clade A and B peptide pools matched to the vaccines
- Seropositivity rates and magnitude of antibody titres to HIV-1 Clade B p17, p24, Nef, RT and F4co as measured by ELISA at indicated time points
- Seropositivity rates and magnitude of anti-Ad35 neutralizing antibody titres at indicated time points

## 5.1.3 Exploratory Endpoints

- Vaccine-specific T-cell response at any of the pre-determined time points to assess both frequency and magnitude of responses measured by:
  - T-cell proliferation frequency and magnitude
  - $\circ~$  T-cell markers for memory, exhaustion and activation, secretion of cytokines other than IFN-  $\gamma$ , IL-2 and TNF- $\alpha$
  - Viral inhibition assay and other possible functional assays

- Vaccine-induced positive reactions measured by SELECTEST (antibody ELISA assay for HIV infection in the presence of vaccine-induced responses) as well as licensed HIV tests
- Number of epitopes recognized by peripheral T cells in selected volunteers
- Anti-Ad35 cell-mediated immune responses at any of the indicated time points by ELISPOT or Intracellular Cytokine Staining (ICS)
- Proportion of volunteers and magnitude of response with HIV-1 specific responses (as measured by ELISPOT, ICS or other assays indicated above) at selected time points after stimulation with HIV-1 Clade C, D or other peptides sets
- Seropositivity rates and magnitude of antibody titres to HIV-1 non-Clade B antigens as measured by ELISA at indicated time points
- Functional antibodies, e.g. avidity or other functional antibody assays at any of the pre-determined time points

## 5.2 Study Design

The study is Phase 1, randomized, placebo-controlled clinical trial designed to evaluate the safety and immunogenicity of F4co formulated in  $AS01_B$  or  $AS01_E$  and Ad35-GRIN. Vaccine or placebo will be administered at 3 separate time points depending on the volunteer's group assignment.

Group	N.,	Months			
Group	(vaccine/ placebo)	0	1	3	4
Α	28/7	F4co 10 μg/ AS01 E	F4co 10 μg/ AS01 E		Ad35-GRIN 2x10  vp
В	28/7	F4co 10 μg/ AS01 B	F4co 10 μg/ AS01 B		Ad35-GRIN 2x10  vp
с	28/7	Ad35-GRIN 2x10  vp		F4co 10 μg/ AS01 B	F4co 10 μg/ AS01 B
D	28/7	F4co 10 μg/ AS01 B Ad35-GRIN 2x10  vp	F4co 10 μg/ AS01 B Ad35-GRIN 2x10  vp		F4co 10 μg/ AS01 B Ad35-GRIN 2x10  vp

Table 1 Study Design

## 5.2.1 Duration of the Study

Volunteers will be screened up to 42 days before vaccination (up to 90 days for Ad35 neutralizing antibody) and will be followed for 12 months after the last vaccination (16 months total participation).

It is estimated that it will take approximately 5 months to complete enrolment.

## 5.2.2 Study Population

The study population consists of healthy male or female adults aged 18 to 40 years who are willing to undergo HIV testing, use an effective method of contraception, and who in the opinion of the investigator or designee, understand the study and provide written informed consent.

Approximately 140 volunteers (112 vaccine /28 placebo recipients) will be included in the study. An over-enrolment of up to 7% (approximately 10 additional volunteers) will be permitted in the study to facilitate rapid enrolment.

## 5.2.3 Inclusion Criteria

- 1. Healthy males and females, as assessed by a medical history, physical exam, and laboratory tests
- 2. At least 18 years of age on the day of screening and has not reached his/her 41st birthday on the day of first vaccination
- 3. Willing to comply with the requirements of the protocol and available for follow-up for the planned duration of the study (screening plus 16 months)
- 4. In the opinion of the Principal Investigator or designee and based on Assessment of Informed Consent Understanding results, has understood the information provided and potential risks linked to vaccination and participation in the trial. Written informed consent needs to be provided by the volunteer before any study-related procedures are performed
- 5. Willing to undergo HIV testing, risk reduction counselling, receive HIV test results and committed to maintaining low risk behaviour for the trial duration
- 6. If a female of childbearing potential (not menopausal or anatomically sterile), willing to use an effective non-barrier method of contraception (hormonal contraceptive; intra-uterine device), from screening until four months after last vaccination. All female volunteers must be willing to undergo urine pregnancy tests at time points as indicated in the Schedule of Procedures (Appendices A, B and C) and must test negative prior to each vaccination.

- 7. If sexually active male (who is not anatomically sterile), willing to use an effective method of contraception (such as consistent condom use) from the day of first vaccination until 4 months after the last vaccination
- 8. Willing to forgo donations of blood or any other tissues during the study and, for those who test HIV positive after vaccination, until the anti-HIV antibody titres become undetectable

## 5.2.4 Exclusion Criteria

- 1. Confirmed HIV-1 or HIV-2 infection
- 2. Any clinically relevant abnormality on history or examination including history of immunodeficiency, malignancy or autoimmune disease; use of systemic corticosteroids (<2 weeks use of topical or inhaled steroids is permitted); immunosuppressive, anticancer, anti-tuberculosis or other medications considered significant by the investigator within the previous 6 months
- 3. Any clinically significant acute or chronic medical condition that is considered progressive, or in the opinion of the investigator, makes the volunteer unsuitable for participation in the study
- 4. Detection of Ad35-specific serum neutralizing antibody
- 5. Reported high-risk behaviour for HIV infection within 6 months prior to first vaccination, as defined by:
  - Unprotected sexual intercourse with a known HIV-infected person, a partner known to be at high risk of HIV infection or a casual partner (i.e. no continuing established relationship)
  - Engaged in sex work for money or drugs
  - Frequent excessive alcohol use, binge drinking (e.g. men consume 5 or more and women 4 or more drinks in about 2 hours) or use of illicit drugs
  - Recently acquired a sexually transmitted disease (STD)
  - A high-risk partner currently or within the previous 6 months
  - Three or more sexual partners

Note: Volunteers with the following behaviour within 6 months prior to first vaccination are eligible:

- Two or fewer mutually monogamous relationships with HIV negative partners who do not use illicit drugs
- Two or fewer partners who were HIV negative, did not use illicit drugs and with whom the volunteer used condoms for sexual intercourse
- 6. If female, pregnant or planning a pregnancy within 4 months after last vaccination; or lactating

- 7. Unstable asthma (e.g. sudden acute attacks occurring without an obvious trigger) or asthma requiring:
  - Daily steroid or long acting  $\beta$  agonist prevention
  - Hospitalization in the last two years
- 8. Bleeding disorder that was diagnosed by a physician e.g., factor deficiency, coagulopathy or platelet disorder that requires special precautions. (A volunteer who states that he or she has easy bruising or bleeding, but does not have a formal diagnosis and has intramuscular (IM) injections and blood draws without any adverse experience is eligible)
- 9. History of splenectomy
- 10. Any of the following abnormal laboratory parameters listed below (laboratory parameters must be consistent with I/E criteria prior to each vaccination):
  - i. Hematology
    - a. Hemoglobin <10.0 g/dL
    - b. Absolute Neutrophil Count (ANC):  $\leq 1000/\text{mm}^3$
    - c. Absolute Lymphocyte Count (ALC):  $\leq$  500/mm^3
    - d. Platelets:  $\leq 90,000/$  mm^3
    - ii. Chemistry
      - a. Creatinine: > 1. 1 x ULN
      - b. AST: >1.25 x ULN
      - c. ALT: >1.25 x ULN
  - iii. Urinalysis: abnormal dipstick confirmed by microscopy
    - a. Protein 2+ or more
    - b. Blood 2+ or more (not due to menses)
    - c. Leukocytes 2+ or more
- 11. Receipt of live-attenuated vaccine within the previous 60 days (live attenuated flu vaccine within 14 days) or planned receipt within 60 days after vaccination with Investigational Product; or receipt of other vaccine (e.g. pneumococcal), allergy treatment with antigen injections or tuberculin skin test within the previous 14 days or planned receipt within 14 days after vaccination with Investigational Product
- 12. Receipt of blood transfusion or blood-derived products within the previous 6 months
- 13. Participation in another clinical trial of an Investigational Product currently, within the previous 3 months or expected participation during this study
- 14. Prior receipt of another investigational HIV vaccine candidate (note: receipt of an HIV vaccine placebo will not exclude a volunteer from participation if documentation is available and the IAVI Medical Monitor gives approval)
- 15. History of severe local or systemic reactogenicity to vaccines (e.g.

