## 6.2 Vaccination Visit

Prior to the vaccination, study staff will:

- Answer any questions about the study
- Review the Informed Consent Document with volunteers
- Review screening safety laboratory data
- Conduct HIV risk assessment
- Conduct HIV risk reduction counselling
- Conduct pre- and post-HIV test counselling
- Conduct family planning counselling
- Review interim medical history
- Collect concomitant medication information
- Perform a symptom-directed physical examination and any further examination indicated by history or observation
- Record vital signs (pulse, respiratory rate, blood pressure and temperature)
- Perform baseline local and systemic reactogenicity assessment of the site of vaccination
- Collect specimens for all tests as indicated in the Schedule of Procedures (Appendices A, B and C). Obtain pregnancy test results prior to vaccination.

The volunteer will be assigned an allocation number according to the instructions specified in the Study Operations Manual.

The Investigational Product will be administered as specified in Section 8.4, Administration of Investigational Product.

For the first 20 volunteers enrolled and vaccinated, study staff will closely observe volunteers for at least 4 hours after first vaccination for any acute reactogenicity. For the remaining volunteers, study staff will closely observe volunteers for at least 30 minutes after vaccination. At the end of the observation period study staff will:

- Record vital signs (pulse, respiratory rate, blood pressure and temperature)
- Assess any local and systemic reactogenicity
- Assess any other adverse events.

For subsequent vaccination visits, study staff will perform the same procedures as above with the following exceptions:

- Review the routine safety laboratory parameters (9.1.6) from the previous visit prior to each vaccination. If a volunteer has an abnormal laboratory value that is known at the time of vaccination, follow the specified guidelines (Section 12.0)
- Conduct pre HIV-test counselling if an HIV Test is required (Appendices A, B and C) or provide post-test counselling if the results of a prior HIV test are being provided to the volunteer.
- All volunteers will be observed for at least 30 minutes after vaccination

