# 12.0 DISCONTINUATION OF VACCINATIONS AND/OR WITHDRAWAL FROM STUDY

## 12.1 Discontinuation of Vaccinations

Any volunteer discontinuing from further vaccinations or being considered for discontinuation of vaccinations will be discussed with the sponsor. Volunteers will be discontinued from further vaccination for any of the following reasons:

- 1. Pregnancy
- 2. Intercurrent HIV Infection
- 3. Use of systemic corticosteroids, immunosuppressive, antiviral, anticancer, antituberculosis or other medications considered significant by the investigator
- 4. A disease or condition or an adverse event that may develop, regardless of relationship to the Investigational Product, if the principal investigator or designee is of the opinion that further study vaccinations will jeopardize the safety of the volunteer
- 5. Any of the following current abnormal laboratory parameters which are known at the time of vaccination:

Haematology

- Haemoglobin <9.0 g/dL or <1.40 mmol/L
- Absolute Neutrophil Count (ANC): < 1000/mm3 or < 1.0 x  $10^{9}$ /L
- Absolute Lymphocyte Count (ALC):  $\leq$  500/mm3 or  $\leq$  0.5 x 10^9/L
- Platelets:  $\leq 90,000 \geq 550,000/\text{mm3} \text{ or } \leq 90 \times 10^9 \geq 550 \times 10^9/\text{L}$

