## Chemistry

- Creatinine: >1.4 x ULN
- AST: >3.0 x ULN
- ALT: >3.0 x ULN

Urinalysis: Dipstick 3+ confirmed by microscopy for

- Protein
- Blood (not due to menses)
- Leukocytes
- 6. Receipt of live attenuated vaccine within the previous 60 days (live attenuated flu vaccine within 14 days) or planned receipt within 60 days after vaccination with Investigational Product or receipt of other vaccine within the previous 14 days or planned receipt within 14 days after vaccination with Investigational Product
- 7. A Grade 4 local reactogenicity event (as per Appendix D) involving the injected arm
- 8. Anaphylaxis; bronchospasm; laryngeal oedema; convulsions or encephalopathy following study vaccinations.
- 9. Life threatening adverse event following study vaccinations unless not related to the Investigational Product and fully resolved.
- 10. Any immediate hypersensitivity reaction judged to be related to the Investigational Product, if the principal investigator or designee is of the opinion that further study vaccinations will jeopardize the safety of the volunteer
- 11. Volunteer requests to discontinue further vaccination.
- 12. Participating in another clinical study of an Investigational Product

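### Exclusion criterion 10 and section 12.1 set different laboratory limits for doses after the first, and no text says which governs

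*Protocol*

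**What the plan says.** Four places in the Protocol bear on whether a volunteer with an abnormal laboratory value may receive the next dose.

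- **Section 5.2.4, exclusion criterion 10**, lists laboratory limits and adds that "laboratory parameters must be consistent with I/E criteria prior to each vaccination". Its limits include "Hemoglobin <10.0 g/dL", "Creatinine: > 1. 1 x ULN" and "ALT: >1.25 x ULN".
- **Section 12.1, item 5**, lists reasons for stopping further vaccination and introduces its laboratory limits as "Any of the following current abnormal laboratory parameters which are known at the time of vaccination". These include "Haemoglobin <9.0 g/dL or <1.40 mmol/L" and "Creatinine: >1.4 x ULN". For AST and ALT the limit is above 3.0 x ULN.
- **Section 6.2**, in the exceptions for subsequent vaccination visits, has staff review the safety laboratory results from the previous visit. If an abnormal value is known, they are to "follow the specified guidelines (Section 12.0").
- **Section 10.5** likewise sends an adverse event or abnormal laboratory value known at vaccination to section 12.0.

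Neither 6.2 nor 10.5 mentions criterion 10, and section 12 does not refer back to it.

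**The concern.** The two lists address the same decision, which is whether to give a dose after the first, and they do not agree. A site working from the eligibility criteria would withhold a dose that a site working from section 6.2 would have no stated laboratory reason to withhold.

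The situation can be expected to arise, because haematology, chemistry and urinalysis are scheduled between doses in Appendices A to C and are reviewed before each vaccination. Safety is a primary objective of this multi-centre Phase I trial. Two sites could therefore treat identical results differently, and whether a given dose counts as a protocol deviation would depend on which section is consulted. Who completes the regimen would depend on it too.

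**Working it through.** The Protocol states no figure that could be reproduced here. The check sets the two lists side by side and runs test values through both.

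| Test | Criterion 10: barred if | 12.1 item 5: stopped if | Fails criterion 10 only |
|---|---|---|---|
| Haemoglobin | <10.0 g/dL | <9.0 g/dL | 9.0 to <10.0 g/dL |
| Creatinine | >1.1 x ULN | >1.4 x ULN | >1.1 to 1.4 x ULN |
| AST, ALT | >1.25 x ULN | >3.0 x ULN | >1.25 to 3.0 x ULN |
| Dipstick protein, blood, leukocytes (confirmed by microscopy) | 2+ or more | 3+ | 2+ |
| Neutrophils (ANC) | ≤1000/mm3 | <1000/mm3 | exactly 1000/mm3 |
| Lymphocytes (ALC) | ≤500/mm3 | ≤500/mm3 | none |
| Platelets, low | ≤90,000/mm3 | ≤90,000/mm3 | none |
| Platelets, high | no limit | ≥550,000/mm3 | none (12.1 only) |

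The widest gap is for AST/ALT, where the limits differ by a factor of 3.0 / 1.25 = 2.4.

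Test cases before a later dose, with all other values normal:

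- Haemoglobin 9.5 g/dL: 9.5 < 10.0, so criterion 10 bars. 9.5 is not < 9.0, so 12.1 item 5 does not stop.
- Creatinine 1.25 x ULN: 1.25 > 1.1, so criterion 10 bars. 1.25 is not > 1.4, so 12.1 item 5 does not stop.
- AST 2.0 x ULN: 2.0 > 1.25, so criterion 10 bars. 2.0 is not > 3.0, so 12.1 item 5 does not stop.
- AST 3.5 x ULN: both lists apply.

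On the Appendix D grading for HIV-negative adults, haemoglobin 9.0 to 9.9 g/dL is Grade 2. AST/ALT from 1.25 to 3.0 x ULN covers Grade 1 (to 2.5) and the lower part of Grade 2 (from 2.6). Creatinine of 1.1 to 1.3 x ULN is Grade 1, and 1.4 is the start of Grade 2.

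Section 12.1 does not name doses 2 and 3. That it concerns doses after the first follows from its scope, further vaccination, and from the pointer in 6.2, which stands among the rules for subsequent visits.

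The haemoglobin comparison uses g/dL because the molar figure in 12.1 is itself out of line with Appendix D. There the HIV-negative Grade 2 range starting at 9.0 g/dL is given as 5.55 mmol/L. The 1.40 in 12.1 matches the conversion factor that Appendix D says was replaced (9.0 x 0.155 = 1.395). With the current factor, 1.40 mmol/L would be 1.40 / 0.6206 = 2.26 g/dL.

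**The case against.** The best defence is that the lists do different jobs and can both be obeyed. Section 12.1 lists mandatory stops and never says that a volunteer outside the list may be dosed. Criterion 10 would then be a condition for each dose, with the dose held until it is met, and 12.1 would mark the point of permanent discontinuation. Section 7.6 allows an additional sample after an abnormal value, which fits this reading. Item 4 of 12.1 also lets the investigator stop vaccination on safety grounds. Any volunteer considered for discontinuation must be discussed with the sponsor, and section 17.1 provides weekly safety review during the vaccination phase.

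Part of this stands. A reader might infer that the same result is both forbidden and permitted. That goes too far, because 12.1 grants no express permission. A reader might also see the upper platelet limit as a conflict in the opposite direction. It is only an additional stop, since criterion 10 is silent on high counts and authorises nothing. The oversight arrangements make unnoticed divergence between centres less likely, so it cannot be asserted that centres will in fact differ.

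The defence does not remove the problem. The hold-versus-stop reading is written nowhere. The only repeat-test provision tied to eligibility, in section 6.1, concerns screening. Vaccination visits after the first have windows of ±3 days, and no rule covers holding a dose for a laboratory value. Where the Protocol intends deferral it says so, as with the corticosteroid washout in section 9.1.5. Item 4 is discretionary and does not restore criterion 10's limits. A site that follows 6.2 and 10.5 literally could therefore dose a volunteer whom criterion 10 bars.

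**Conclusion.** The inconsistency is real and should be corrected. It is material for haemoglobin, creatinine, AST/ALT and dipstick, trivial for neutrophils, and absent for lymphocytes and low platelets. It rests on the wording of the four sections and needs no outside assumption.

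A reader might go on to infer a loss of power for the non-inferiority comparison, which section 14.2.2 sizes at 27 per group against 28 vaccinees planned. The documents do not support that. They give no frequency for values between the two lists, so any number of volunteers lost would be invented. Only dose 2 in Groups A and B bears on that comparison, and over-enrolment of up to 7% is allowed. Groups A and B also share one schedule and are blinded to each other, so no route to bias between them is apparent. The effect on the number of volunteers with two F4co doses is unknown, and the point stands as a safety rule that can be applied in two ways.

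**What to change.** Amend sections 5.2.4 (criterion 10), 6.2, 10.5 and 12.1 (item 5) together so that:

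- one stated rule governs laboratory eligibility for vaccinations after the first, with criterion 10's wording and the references in 6.2 and 10.5 matching it;
- the text says whether a value between the two present lists leads to a hold, with its repeat-test and timing provisions, or to discontinuation;
- the neutrophil boundary, the upper platelet limit and the haemoglobin unit conversion are aligned in the same edit.

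Which limits apply, and what follows from an in-between value, is for the clinical team to decide. The cost is amendment wording and notice to the sites. The relevant tests are already scheduled, so no new assessment is needed.
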